4.7.3 Additional safety assessments

4.7.3.1 Laboratory variables, vital signs and electrocardiograms (ECGs)

The following laboratory variables, vital signs and electrocardiogram (ECG) variables will be analyzed. They will be converted into standard international units.

- Hematology
 - **Hemoglobin and coagulation:** hemoglobin, prothrombin time (PT), activated partial thromboplastin time, fibrinogen, D-dimer and international normalized ratio (INR)
 - **Platelet count**
 - **White blood cells:** white blood cells (WBC) count, neutrophils, lymphocytes, monocytes, basophils, eosinophils, leukocytes
 - **Hematocrit**
 - **Blasts**
- Biochemistry
 - **Electrolytes:** sodium, potassium, calcium, phosphate, bicarbonate/carbon dioxide, albumin, protein, magnesium
 - **Renal function:** serum creatinine, estimated creatinine clearance by Cockcroft-Gault formula, blood urea nitrogen (BUN), uric acid

- **Liver parameters:** alanine aminotransferase (ALT), aspartate aminotransferase (AST), alkaline phosphatase, lactate dehydrogenase (LDH), gamma glutamyl transpeptidase (GGT), total and direct bilirubin
- Urinalysis
 - **Qualitative urinalysis:** protein, glucose, pH
- Pregnancy: urine, serum
- Serology: hepatitis B virus surface antigen, hepatitis C virus antibody
- Pro-inflammatory cytokines, CRP, and ferritin
- Cytogenetic/FISH data collection
- Vital signs: heart rate, systolic and diastolic blood pressure, respiratory rate, oxygen saturation, weight, body surface area (BSA), temperature and ECOG PS (0, 1, 2, 3, 4).
- ECG

Data below the lower limit of quantitation/detection limit (LLOQ) will be replaced by half of the LLOQ, data above the upper limit of quantification (ULOQ) will be replaced by ULOQ value.

For hematological parameters and some selected biochemistry parameters, Sanofi generic ranges (LLN, ULN) are defined and will be used for grading. For other biochemistry parameters, grading will be derived using local laboratory normal ranges.

Analyses according to potentially clinically significant abnormality (PCSA) and NCI CTCAE grading

For laboratory variables, analyses according to NCI grading will be made based on NCI-CTCAE version specified in the protocol.

Analyses according to NCI CTCAE grading will be performed based on the worst value during the treatment-emergent period, using all measurements (either local or central, either scheduled, nonscheduled or repeated).

In addition, for basophils, eosinophils, monocytes, creatinine clearance, eGFR, hematocrit, uric acid, PH, uric acid, blood urea nitrogen, potentially clinically significant abnormality (PCSA) analyses will be performed based on the PCSA list currently in effect at Sanofi at the time of the database lock.

For laboratory variables above, vital signs and ECG variables, the incidence of participants with at least one PCSA during the treatment-emergent period will be summarized regardless of the baseline level and according to the following baseline status categories:

- Normal/missing
- Abnormal according to PCSA criterion or criteria

For laboratory variables graded by NCI-CTCAE,

- The number (%) of participants with abnormal laboratory tests at baseline will be presented by grade.
- The number (%) of participants with abnormal laboratory tests during the treatment-emergent period will be summarized by grade. When appropriate, the number (%) of participants with abnormality of any grade and with Grade 3-4 abnormalities will be provided.

4.8 OTHER ANALYSES

4.8.1 PK analyses

Pharmacokinetic parameters of SAR440234 will be analyzed under the responsibility of Sanofi, Pharmacokinetics, Dynamics and Metabolism (PKDM) department. Pharmacokinetic parameters will be determined by non-compartmental analysis using PKDMS V3.1 (running Phoenix software).

The PK parameters will include, but may not be limited to the following:

Parameters	Definition/calculation
C_{eoI}	Concentration observed at the end of intravenous infusion
C_{max}	Maximum concentration observed
t_{max}	Time to reach C_{max}
C_{last}	Last concentration observed above the lower limit of quantification
t_{last}	Time of the last concentration observed above the lower limit of quantification (ie, C_{last})
C_{through}	Concentration observed just before treatment administration during repeated dosing
AUC_{last}	Area under the plasma concentration versus time curve calculated using the trapezoidal method from time zero to time of the last concentration observed above the lower limit of quantification (ie, C_{last})
AUC	Area under the concentration versus time curve calculated using the trapezoidal method from time zero to time infinity according to: $AUC = AUC_{\text{last}} + C_{\text{last}}/\lambda z$ where λz is the slope of the regression line of the observed terminal phase of the concentration versus time curve, in semi-logarithmic scale
AUC_{0-T}	Area under the concentration versus time curve calculated using the trapezoidal method during a dosing interval (T)

Descriptive statistics (arithmetic mean, standard deviation, geometric mean, coefficient of variation (%), median, minimum and maximum) for concentrations and PK parameters of SAR440234 as well as associated plots will be provided by Sanofi, PKDM.

All concentration values below the lower limit of quantitation (LLOQ) will be treated as zero in all summary statistics.

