### 1.3 PHARMACOKINETIC, PHARMACODYNAMIC, BIOMARKER AND IMMUNOGENICITY FLOW CHARTS

# 1.3.1 Cycle 1: Week 1

	Camaamima							Сус	cle 1						
Week within Cycle	Screening							We	ek 1						
Day within Cycle	D-14 to D-1					Day 1					D	ay 4 (Week	1 Dose Le	vels ≥3 on	ly)
Time (decimal hours)		SOI	EOI	EOI +1h	EOI +2h	EOI +5h	EOI +7h	EOI +24h	EOI +48h	72h a, e	SOI	EOI	EOI +2h	EOI +5h	EOI +24h
Indicative clock time (based on a 2h infusion)	8:00 AM	8:00 AM	10:00 AM	11:00 AM	12:00 PM	3:00 PM	5:00 PM	10:00 AM	10:00 AM	8:00 AM	8:00 AM	10:00 AM	12:00 AM	3:00 PM	10:00 AM
Treatment (IV infusion	)														
SAR440234		X	X								X	X			
Pharmacokinetics															
SAR440234 b, c, d		P00€	P01 f	P02	P03	P04	P05	P06	P07	P08 a, e		P09 f, g	P10 	P11 	P12 
Immunogenicity															
ADA b, c, d		AB00 e													
Biomarkers															
Cytokines b, c, i, j	CS00	C00e	C01 f	C02	C03	C04	C05	C06	C07	C08 a , e		C09 f,g	C10 	C11 	C12 

- a Sample to be drawn immediately before starting the next infusion if the patient is continuing to be treated in the study and there is no dose delay.
- b Refer to laboratory manual for sample collection, processing, and shipping.
- c The sampling time-points for PK, ADA and cytokines may be modified during the course of the study (ie, omitting samples) based on the updated knowledge of SAR440234 behavior.
- d Sampling for PK analysis and ADA detection will be stopped in all patients at the second study cut-off date.
- e Pre-dose samples to be collected strictly before start of SAR440234 infusion.
- f End of infusion sample to be collected within 10 minutes before the actual end of infusion.
- g Samples to be collected from Dose Level 3.
- h Mid of infusion sample to be collected during SAR440234 infusion only for infusion length  $\geq 5$  hours.
- i An additional sample (CA00, CA01...) must be collected in case of Grade ≥2 CRS if it occurs, or as soon as it is diagnosed.
- *j* CRP/ferritin will be measured at the same times as cytokines.

Abbreviations: AB=antibody, ADA=anti-drug antibody (ie, anti-SAR440234 antibody), C=cytokines, CRS=cytokine release syndrome, CS=cytokines screening, EOI=end of infusion, h=hours, IV=intravenous, P=plasma, PK=pharmacokinetic, SOI=start of infusion

### 1.3.2 Cycle 1: Week 2 and Week 3

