# 4.4 PHARMACOKINETICS IN ANIMAL

The nonclinical pharmacokinetics of SAR440234 were investigated in the toxicological species (cynomolgus monkeys) following an IV (1-hour infusion) administration of H-SAR440234 to overcome the limitation of the immunoassay sensitivity. Following a single IV (1 hour) administration to cynomolgus monkeys, the radioactivity exhibited a bi-compartmental pharmacokinetic profile. The volume of distribution ranged from and clearance ranged from . Terminal elimination half-life was around Exposure assessed by area under the curve (AUC) increased slightly less than expected by dose increase, with a increase in AUC for a increase in dose.

As the drug substance is a therapeutic protein, no other evaluation was conducted for absorption, distribution, elimination or excretion. It is generally recognized that antibodies are metabolized by degradation into small peptides and individual amino acids following endogenous catabolism, therefore no metabolism studies were conducted.

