# 13.4.5 Analyses of pharmacokinetic variables

Individual concentrations and pharmacokinetic parameters of SAR440234 will be summarized by descriptive statistics (such as mean, geometric mean, median, SD, standard error of the mean, coefficient of variation, minimum, and maximum). Individual and mean profiles will be presented graphically. Dose proportionality and accumulation will also be assessed on relevant parameters in the pharmacokinetic population.

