4.8.3 Biomarker analyses

Plasma levels of pro-inflammatory cytokines, including interleukin-6 and interferon- γ , as well as blood levels of 2 acute phase proteins, C-reactive protein (CRP) and ferritin, will be assessed during the trial.

Several immune populations and sub-populations will be assessed through immunophenotyping performed on blood and bone marrow samples. Different panels will be investigated such as the blasts, the plasmacytoid dendritic cells and basophils, the T cells, and the NK cells, granzyme B and interferon- γ , as well as analysis of T cell functional status including frequency of Tregs (CD4+CD25+CD127-) and expression of activation markers such as PD-1 and CD25.

All biomarkers will be summarized by dose level at baseline and over time by using descriptive statistics. For cytokines, the number of values below the LLOQ will be provided and for the computation of summary statistics, LLOQ/2 will be used to impute the test results with below LLOQ (BLOQ, ie, value<LLOQ).

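### SAP 4.8.1 sets PK concentrations below LLOQ to zero in every summary statistic but also requires the geometric mean, which a single zero makes zero or undefined

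*SAP*

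**What the plan says.** SAP 4.8.1 lists the statistics to be produced: "Descriptive statistics (arithmetic mean, standard deviation, geometric mean, coefficient of variation (%), median, minimum and maximum) for concentrations and PK parameters of SAR440234". After that comes the rule for values that cannot be quantified: "All concentration values below the lower limit of quantitation (LLOQ) will be treated as zero in all summary statistics". The section names no statistic to which the rule does not apply.

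Protocol 13.4.5 also includes the geometric mean: "Individual concentrations and pharmacokinetic parameters of SAR440234 will be summarized by descriptive statistics (such as mean, geometric mean, median, SD, standard error of the mean". It gives no rule for values below LLOQ, so it does not settle the matter.

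Elsewhere the SAP does something different. For cytokines (4.8.3), "LLOQ/2 will be used to impute the test results with below LLOQ", and the number of such values is reported. For laboratory data (4.7.3.1) half the LLOQ is also substituted. The PK section asks for no count of values below LLOQ.

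**The concern.** A geometric mean needs strictly positive values. If the two instructions in 4.8.1 are followed literally, the geometric mean carries no information wherever one patient is below LLOQ: it shows 0 or a missing value however high the other concentrations are.

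Some values below LLOQ are foreseeable. The PK flow chart in Protocol 1.3.1 has a sample before the first infusion ("Pre-dose samples to be collected strictly before start of SAR440234 infusion"), when no drug has been given. Ctrough is itself a pre-dose concentration ("Concentration observed just before treatment administration during repeated dosing"). Dosing starts at 1 ng/kg.

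What is at stake is the quality of a descriptive secondary output. A programmer facing this text has three choices: print 0, print missing, or adopt an unstated convention. As the working shows, two reasonable conventions can differ by a factor of about two in a cohort of three.

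**Working it through.** The plan gives no figure to reproduce here. The check is whether the two instructions can both be followed, and which outputs are touched.

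**Inputs from the documents**
- Geometric mean required for concentrations and PK parameters; zero rule for all summary statistics (SAP 4.8.1).
- Summaries by part, by dose level and overall, where applicable (SAP 4.1).
- Cohorts of 3 patients, or 6 if expanded (Protocol 6.2.2). The PK population is treated patients with at least one post-baseline concentration (SAP section 3), so n in a PK table can differ from these cohort sizes.

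**Assumed inputs, for illustration only**
- LLOQ = 1 in arbitrary units; quantifiable values as shown below.

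**Step 1: effect of one zero.** In product form, GM = (x1 × x2 × … × xn)^(1/n). In log form, GM = exp(mean of log x).

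*n = 3, values 4, 5 and one below LLOQ*
- SAP rule: (4 × 5 × 0)^(1/3) = 0. In log form, log 0 is minus infinity and the SD of the logs cannot be computed.
- LLOQ/2: (4 × 5 × 0.5)^(1/3) = 10^(1/3) = 2.15.
- Quantifiable values only: (4 × 5)^(1/2) = 4.47.
- With the zero kept, the arithmetic mean is 9/3 = 3.0 and the median is 4.0.

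*n = 6, values 4, 5, 6, 7, 8 and one below LLOQ*
- SAP rule: 0.
- LLOQ/2: (6720 × 0.5)^(1/6) = 3.87.
- Quantifiable values only: 6720^(1/5) = 5.83.
- With the zero kept, the arithmetic mean is 30/6 = 5.0 and the median is 5.5.

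The zero rule is therefore workable for the arithmetic mean and median and fails only for the geometric mean and any log-scale CV. SAP 4.8.1 does not say whether its CV is arithmetic or geometric.

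**Step 2: which outputs are touched**
- Directly: concentration summaries at each time point; Ctrough; Ceoi or Cmax in a patient for whom that value is below LLOQ.
- Not directly: Clast, which SAP 4.8.1 defines as a value above LLOQ, and AUClast, which runs to the time of Clast.

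**Step 3: sensitivity to the rate below LLOQ.** If each patient's value at one time point is below LLOQ independently with probability q, the chance of at least one is 1 − (1 − q)^n. The documents give no q, so a range is assumed.

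| Assumed q | n = 3 | n = 6 |
|---|---|---|
| 5% | 14% | 27% |
| 10% | 27% | 47% |
| 20% | 49% | 74% |
| 30% | 66% | 88% |
| 50% | 88% | 98% |

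This shows only how sensitive a small cohort is to one value. It does not estimate how often the problem will occur.

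**The case against.** The best case against the point is that little depends on it. The arithmetic mean, median, minimum and maximum remain computable, and Protocol 13.4.5 also provides for individual profiles. No decision rule or test in either document uses the geometric mean. All of this stands, and it keeps the point minor.

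Four stronger readings are tempting, and the documents do not support them.

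- *That dose selection is compromised.* Protocol 6.3 lets PK help define the recommended dose, but that is a decision taken during the trial. This SAP was written after early termination: sections 4.3 and 4.4 drop the efficacy analyses, 4.6 plans no formal testing, and 4.9 drops the interim analysis.
- *That the protocol shows patient samples will often be below LLOQ.* The remark in Protocol 4.4 about the need to "overcome the limitation of the immunoassay sensitivity" concerns the monkey PK study, where a radiolabel was used. Clinical samples are assayed by a validated method (Protocol 9.2.3) whose LLOQ is not stated, and the higher dose levels are redacted.
- *That about half or more of the time points are affected.* Any such figure rests on an assumed q with no source. Rates would also vary by time point: near 100% before the first dose, where a geometric mean tells the reader nothing under any rule, and probably lowest at the end of infusion.
- *That the SAP contradicts itself by using LLOQ/2 elsewhere.* Different conventions for endogenous analytes and for an administered drug are not a contradiction. The cytokine rule only shows that the sponsor already has a workable convention.

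None of this removes the core defect. The required statistic and the zero rule stand together in one section, and following both yields an uninformative number.

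**Conclusion.** The point holds, at low severity. As written, SAP 4.8.1 produces a geometric mean of zero, or none at all, for any concentration time point or concentration-based parameter with at least one value below LLOQ. This follows exactly from the text and needs no assumption. The numbers in the illustration rest on an assumed LLOQ and assumed concentrations, and the frequency table on an assumed rate and on independence between patients. The true frequency cannot be derived from the documents. The consequence is confined to the descriptive PK tables.

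**What to change.** Amend SAP 4.8.1 as follows:

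1. Limit the zero rule to the arithmetic mean, SD, median, minimum and maximum.
2. Report the number of values below LLOQ beside each summary.
3. State one rule for the geometric mean and any log-scale CV. Either LLOQ/2, as already used for cytokines, or quantifiable values only with their n shown, would serve.
4. Mark the geometric mean as not calculated where it would be uninformative, for example at the first pre-dose sample.

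The cost is a few sentences in the SAP and a small programming change, with no new data. The one drawback is that the arithmetic and geometric means in the same table would rest on different handling of values below LLOQ. A footnote should say so.

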4.8.2 Immunogenicity analysis

The immunogenicity of SAR440234 will be presented for all patients through an individual listing of immunogenicity sample results (positive, negative or inconclusive) together with the associated titer, C_{trough} value, the immunogenicity status of the patient and associated characterization of the immune response (transient, persistent, indeterminate) for positive ones.

The impact of positive immune response will be evaluated on pharmacokinetic, and safety endpoints when relevant.

Participant's ADA status

- Participants with **pre-existing ADAs** correspond to participants with ADAs present in samples drawn before first administration of intervention. Participants with missing ADA sample at baseline will be considered as without pre-existing ADA.
- Participants with **treatment-emergent ADA** correspond to participants with at least one treatment-induced/boosted ADA sample.
 - Participants with **treatment-induced ADAs** correspond to participants with ADAs that developed during the treatment-emergent (TE) period and without pre-existing ADA (including participants without pre-treatment samples).
 - Participants with **treatment-boosted ADAs** correspond to participants with pre-existing ADAs that are boosted during the TE period to a significant higher titer than the baseline. A 2-fold serial dilution schema is used during titration, so at least a 4-fold increase will be considered as significant.
- Participants **without treatment-emergent ADA** correspond to participants without treatment-induced/boosted ADA and without any inconclusive sample during the TE period.
- Participants **with inconclusive ADA** are defined as participants which cannot irrefutably be classified as with or without treatment-emergent ADA.

Kinetics of ADA response

Kinetics of ADA response will be derived for participants with treatment-induced/boosted ADA considering ADA samples collected during the TE period and post-treatment period.

- **Time to onset of ADA response** is defined as the time period between the first IMP administration and the first treatment-induced/boosted ADA.

- **Duration of ADA response** is defined as the time between the first treatment-induced/boosted ADA and the last treatment-induced/boosted ADA, irrespective of negative samples or positive samples not reaching the boosted threshold in-between. ADA duration will be summarized only for participants with persistent ADA response.
 - A positive sample (boosted positive sample for participants with pre-existing ADA) occurring after the TE period will be considered as treatment-induced/boosted ADA if a previous treatment-induced/boosted ADA occurred during the TE period and less than 16 weeks before this sample.
- **Persistent ADA response** is defined by treatment-induced/boosted ADA with a duration of ADA response of at least 16 weeks.
- **Transient ADA response** is defined by treatment-induced/boosted ADA with a duration of ADA response of less than 16 weeks and the last sample is not treatment-induced/boosted.
- **Indeterminate ADA response** is defined by treatment-induced/boosted ADA that are neither persistent nor transient.

ADA response variable:

- **ADA incidence** is defined as the proportion of participants found to have seroconverted (treatment-induced ADAs) or boosted their pre-existing ADA response (treatment-boosted ADAs) at any time point during the TE period.

4.8.3 Biomarker analyses

Plasma levels of pro-inflammatory cytokines, including interleukin-6 and interferon- γ , as well as blood levels of 2 acute phase proteins, C-reactive protein (CRP) and ferritin, will be assessed during the trial.

Several immune populations and sub-populations will be assessed through immunophenotyping performed on blood and bone marrow samples. Different panels will be investigated such as the blasts, the plasmacytoid dendritic cells and basophils, the T cells, and the NK cells, granzyme B and interferon- γ , as well as analysis of T cell functional status including frequency of Tregs (CD4+CD25+CD127-) and expression of activation markers such as PD-1 and CD25.

All biomarkers will be summarized by dose level at baseline and over time by using descriptive statistics. For cytokines, the number of values below the LLOQ will be provided and for the computation of summary statistics, LLOQ/2 will be used to impute the test results with below LLOQ (BLOQ, ie, value<LLOQ).

4.9 INTERIM ANALYSES

Not applicable due to early termination of the clinical trial.

5 SUPPORTING DOCUMENTATION

5.1 APPENDIX 1: LIST OF ABBREVIATIONS

ADA:	anti-drug antibody
ADI:	actual dose intensity
AE:	adverse event
AESIs:	adverse events of special interest
ALT:	alanine aminotransferase
AST:	aspartate aminotransferase
AUC:	area under the curve
B-ALL:	B-cell acute lymphoblastic leukemia
BUN:	blood urea nitrogen
CR:	confirmed response
CRF:	case report form
CRI:	complete response with incomplete hematologic recovery
CRS:	cytokine release syndrome
DL:	dose level
DLT:	dose limiting toxicity
ECG:	electrocardiogram
eCRF:	Electronic case report form
FISH:	fluorescence in situ hybridization, Eastern Cooperative Oncology Group
GGT:	gamma glutamyl transpeptidase
HLT:	high level term
HR-MDS:	high risk myelodysplastic syndrome
IMP:	investigational medicinal product
INR:	international normalized ratio
IV:	intravenous
IWG:	International Working Group
LDH:	lactate dehydrogenase
LLT:	lower-level term
MAD:	maximum administered dose
MDS:	myelodysplastic syndrome
MedDRA:	medical dictionary for regulatory activities
MRD:	minimal residual disease
MTD:	maximum tolerated dose
NCCN:	National Comprehensive Cancer Network
NIMP:	non-investigational medicinal product
ORR:	overall response rate
PD:	pharmacodynamic
PDI:	planned dose intensity
PK:	pharmacokinetic
PR:	partial response
PT:	preferred term

R/R AML:	relapsed or refractory acute myeloid leukemia
RDI:	relative
RP2D:	recommended phase 2 dose
SAE:	serious adverse event
SAP:	statistical analysis plan
SOC:	system organ class
TE:	treatment-emergent
TEAE:	treatment-emergent adverse event
WBC:	white blood cells
WHO-DD:	World Health Organization-drug dictionary

